3.2. Secondary Endpoint(s)

The key secondary endpoint is percentage of all-cause mortality on Day 42 following primary treatment with isavuconazole in participants with IFD.

The other secondary endpoints are for participants with IFD include:

- The percentage of all-cause mortality on Day 84 following primary treatment with isavuconazole.
- The crude rate of overall response based on the investigators' assessment at EOT, Day 42, and 84.
- The crude success rates of the clinical, mycological, radiological responses based on the investigators' assessment at EOT, Day 42 and Day 84.
- Other AE summaries, including TEAE related to study intervention, Treatment-Emergent serious adverse events (SAE), TEAE leading to discontinuation of study intervention, TEAE leading to deaths, and all Deaths.
- Other safety variables including clinical laboratory variables, vital signs, 12-lead ECG and eye examination.
- Isavuconazole plasma concentrations at Day 3, 7, 14 and EOT visit.

3.3. Other Endpoint(s)

The exploratory endpoints include:

- The percentage of all-cause mortality on Days 42 and 84 following primary treatment with isavuconazole in participants with IM.
- The crude rate of overall response at EOT, Day 42, and 84 in participants with IM.
- The crude success rates of the clinical, mycological, radiological responses based on the investigators' assessment at EOT, Day 42 and Day 84 in participants with IM.

CCI

3.4. Baseline Variables

Baseline is defined as the last observation on or prior to the first administration of study medication, unless otherwise specified.

The baseline variables in the study contain demographic and other baseline characteristics as follows.

- Age, Gender, Race, Ethnicity, Country, Height, Weight, Body mass index (BMI)
- Age category 1: ≤ 45 , > 45 to ≤ 65 , > 65
- Age category 2: ≤ 65 , > 65 to ≤ 75 , > 75
- BMI: < 25 , ≥ 25 to < 30 , ≥ 30
- eGFR- CKD-EPI category: < 60 , ≥ 60
- Baseline Neutropenic Status: Yes/No
- Use of T-cell/B-cell immunosuppressant: Yes/No
- Use of Corticosteroids: Yes/No
- Prior allogeneic HSCT/BMT: Yes/No
- Solid organ transplant: Yes/No
- Hematologic malignancy: Yes/No
- Other malignancy: Yes/No
- Chronic respiratory airway abnormality: Yes/No
- Primary diagnosis type: IA, IM, other

Details of derivation for eGFR-CKD-EPI are included in Appendix 2.

Baseline Neutropenic Status will be defined as “Yes” for participants who had Absolute Neutrophil Count (ANC) $< 0.5 \times 10^9/L$ [$< 500/mm^3$] at baseline.

Use of T-cell/B-cell immunosuppressant and Use of Corticosteroids will be determined based on clinical review with the prior medication data collected via CRF.

Prior allogeneic HSCT/BMT, Solid organ transplant, Hematologic malignancy, Other malignancy, and Chronic respiratory airway abnormality will be determined based on clinical review with the medical history data collected via CRF.

3.5. Safety Endpoints

The incidence rates of TEAEs by SOC and PT is the primary endpoint in this study. See Section 3.1. Other TEAE summaries and safety endpoints are secondary endpoints in this study.

3.5.1. Adverse Events

An AE is referred to TEAE in this study unless mentioned otherwise. See Section 3.1 for the definition of TEAE.

An abnormality identified during a medical test (e.g., laboratory parameter, vital sign, ECG data, physical exam) should be defined as an AE only if the abnormality meets one of the following criteria:

- Induces clinical signs or symptoms
- Requires active intervention
- Requires interruption or discontinuation of study medication

The abnormality or investigational value is clinically significant in the opinion of the investigator.

3.5.2. Laboratory Data

The laboratory data includes test values of hematology, biochemistry and urinalysis.

Samples for the full safety profile will be obtained on Screening, Days 1, 7, 14, 28, 42, every 42 days after Day 84, EOT and Follow-up.

The last value of laboratory tests obtained on Day 1 (or 72 hours) prior to the first dose of study intervention will be considered as baseline assessment. Hematology, biochemistry and urinalysis will be performed in local laboratory.

3.5.3. Vital Signs

The following vital signs will be measured at Screening and on Days 1, 7, 14, 42, 84, every 42 days after Day 84, and EOT:

- Systolic blood pressure (mmHg)
- Diastolic blood pressure (mmHg)
- Pulse rate (PR, beats per minute [bpm])
- Respiratory rate (times per minute)
- Body temperature (°C, oral)

If participants discontinue from study intervention prior to Day 7, the assessments on Days 7 and 14 on vital signs are not required. At the Follow-up visit, vital signs will only be obtained from participants with abnormalities observed at the previous visit.

The vital signs assessment obtained on Day 1 prior to the administration of study intervention will be considered as baseline value.

3.5.4. Twelve-lead Electrocardiogram

The electrocardiogram (ECG) measurements will include the following: Heart Rate (bpm), PR interval (msec), QTc (corrected QT) interval (msec), QRS (msec), QT (msec). Those measurements will be obtained at Screening and will also be performed on Day 1, Days 7, 14, 42, 84, every 42 days after Day 84, and EOT while the participant remains on study intervention. All participants will have an ECG at EOT. At the Follow-up visit, ECG will only be obtained from participants with abnormalities observed at EOT.

The last ECG measurement obtained at Screening visit prior to the administration of study intervention will be considered as baseline value.

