Radiology assessment (CT/HRCT/MRI)	X ^s		X ^o			X ^l	X ^l	X	X	X	
Bronchoscopic assessment ^l	X ^l		X ^o			X ^l	X ^l	X ^l	X ^l	X ^l	
Mycological assessment (Microbiology/Histopathology/Cytopathology/Tissue Nucleic Acid)	X			X ^l				X	X	X	
Neutropenic status/ANC	X		X Ongoing-----								→
Survival status ^k			X Ongoing-----								→

- Day related to start of study treatment (Day 1), Day -1 can be the same calendar day as Day 1.
- Anti-infective history taken within 4 weeks prior to the first dose of study intervention will be collected in the eCRF.
- All medication (except for anti-infective agents, T-cell & B-cell immunosuppressants and corticosteroids) given within 2 weeks prior to the first dose of study intervention will be collected in eCRF. T-cell & B-cell immunosuppressants given within 3 months prior to the first dose of study intervention, anti-infective agents and corticosteroids given within 4 weeks prior to the first dose of study intervention will be collected in eCRF.
- A serum β-hCG testing should be performed at screening for all WOCBP according to [Section 8.3.6](#). A negative serum or urine β-hCG test must be obtained before the first dose of study intervention.
- Samples/assessments obtained within 72 hours prior to the first dose of study intervention could be accepted as the Day 1 results.
- Study intervention administration will occur every day from Day 1 to Day 84 (Day 180 for IM) or EOT.
- Adverse events will be recorded from the sign-off of informed consent to at least 28 days after last dose of study intervention.
- Only in participants with abnormalities observed at EOT.
- On Day 1, vital signs will be measured within 1 hour before and 1 hour after the end of each study intervention administration.

Period	Screening	Study Treatment									Follow-Up
Visit Identifier	Screening D-7 to D-1	Day 1	Day 2 ^p	Day 3 ^p	Day 7 ^p	Day 14 ^p	Day 28 ^p	Day 42 ^k	Day 84 ^{k,q} /Every 42 days after Day 84 ^q	End of Treatment (EOT) ^{k,m} or Discontinuation	Post Treatment Follow-up ^k (4 weeks after EOT)
Visit Window (Day) ^a					±2	±3	±3	±7	±7	±3	±7

- j. Measuring once prior to study intervention administration.

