- k. EOT, Day 42, Day 84 and Follow-up assessments are required for all participants. Participants with a successful overall response are required to return for all these visits. Participants withdrawn from study intervention or with an unsuccessful overall response prior to Day 42 are required to return to conduct a clinic visit for the EOT visit but will not be asked to return for the Day 42 or Day 84 visits; however, the participant will be contacted by telephone to obtain survival status at these time points. For participants with IM, survival status on Day 126, Day 168 and Day 180 should be collected. A Follow-up visit will be performed 4 weeks (± 7d) after last dose of isavuconazole administration.
- l. If clinically indicated.
- m. If EOT occurs within 1 week of a scheduled visit, the visits and assessment can be combined; however, the schedule of assessments for EOT must be applied.
- n. 12-lead ECG is performed 15 minutes prior to the end of the first daily infusion or approximately 3 hours post oral dose during the treatment period.
- o. If the assessments are performed at screening, the additional assessments between Day 1 and Day 7 are not required.
- p. Applicable for participants continuing on study intervention.
- q. For participants with IA or other filamentous fungi infection other than IM, if study treatment needs to be extended to longer than 84 days, sponsor should be notified. For participants with IM, procedures on Day 84, Day 126 and Day 168 should follow requirements of Day 42, maximum of study treatment is 180 days or until EOT visit.
- r. GM antigen will be tested at screening. If clinically indicated, it can be tested during Day 1 to Day 7 for participants with IA only. Any 1 of the following: 1) A single serum or plasma value ≥ 1.0 ; 2) BAL fluid ≥ 1.0 ; 3) single serum or plasma: ≥ 0.7 and BAL fluid ≥ 0.8 ; 4) two consecutive values of either serum, plasma or BAL fluid between ≥ 0.5 to <1.0 (from two separate specimens of the same category) is considered a positive result. GM meeting the protocol defined requirements within 7 days prior to first dose of study drug are eligible for enrollment.
- s. Radiology imaging obtained within 1 week (if available) prior to screening could be used.
- t. Samples/assessments obtained within 72 hours prior to screening could be used.

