8.3.3. Electrocardiograms

Twelve-lead ECG recordings will be obtained at Screening and will also be performed on Day 1, Days 14, 42, 84 and EOT, while the participant remains on study intervention. All participants will have an ECG at EOT.

Standard 12-lead ECGs should be collected on visits specified in the [SoA](#) using an ECG machine that automatically calculates the HR and measures PR, QT, QTc intervals and QRS complex. Each ECG recording is to be signed and dated by the investigator or his designee. Abnormalities, if not related to the underlying disease, must either be confirmed as clinically not significant or are to be repeated until they have returned to baseline levels. Abnormalities should not be reported as AEs on the AE page of the eCRF unless they result in a clinically relevant condition.

All scheduled ECGs should be performed after the participant has rested quietly for at least 10 minutes in a supine position.

If a) a post-dose corrected QT (QTc) interval remains ≥ 30 msec from the baseline **and** is >450 msec; or b) an absolute QTc value is ≥ 500 msec for any scheduled ECG for greater than 4 hours (or sooner, at the discretion of the investigator), or c) QTc intervals get progressively longer, the participant should undergo continuous ECG monitoring. A cardiologist should be consulted if QTc intervals do not return to less than the criteria listed above after 8 hours of monitoring (or sooner, at the discretion of the investigator).

In some cases, it may be appropriate to repeat abnormal ECGs to rule out improper lead placement as contributing to the ECG abnormality. It is important that leads be placed in the same positions each time in order to achieve precise ECG recordings. If a machine-read QTc value is prolonged, as defined above, repeat measurements may not be necessary if a qualified medical provider's interpretation determines that the QTc values are in the acceptable range.

ECG values of potential clinical concern are listed in [Appendix 7, Section 10.7](#).

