Appendix 3. Analysis window for efficacy and safety endpoints

Investigator Assessments	Visits	Scheduled Day	Window in Days
Clinical and Mycological	Day 42	42	2 to 49
	Day 84	84	50 to 91
	Day 126	126	92 to 133
	Day 168	168	134 to 175
Radiological	Day 42	42	8 to 49
	Day 84	84	50 to 91
	Day 126	126	92 to 133
	Day 168	168	134 to 175
Clinical, Mycological and Radiological	EOT	Last Dose Day	Closest to Last Dosing Day

Safety Assessments	Visits	Scheduled Day	Window in Days
Laboratory Tests for both IA and IM	Day 1	1	1
	Day 7	7	2 to 9
	Day 14	14	10 to 20
	Day 28	28	21 to 34
	Day 42	42	35 to 63
	EOT	Last Dose Day	Closest to Last Dosing Day
	Follow Up	Nominal Follow up Visit	NA
Laboratory Tests for IM	Day 84	84	64 to 105
	Day 126	126	106 to 147
	Day 168	168	148 to 201

Safety Assessments	Visits	Scheduled Day	Window in Days
Vital Signs for both IA and IM	Day 1	1	Using CRF Day/Time
	Day 7	7	2 to 9
	Day 14	14	10 to 28
	Day 42	42	29 to 63
	Day 84	84	64 to 105
	EOT	Last Dose Day	Closest to Last Dosing Day
	Follow Up [#]	Nominal Follow up Visit	NA
Vital Signs for IM	Day 126	126	106 to 147
	Day 168	168	148 to 201
ECG for both IA and IM	Day 1	1	1
	Day 7	7	2 to 9
	Day 14	14	10 to 28
	Day 42	42	29 to 63
	Day 84	84	64 to 105
	EOT	Last Dose Day	Closest to Last Dosing Day
	Follow Up [#]	Nominal Follow up Visit	NA
ECG for IM	Day 126	126	106 to 147
	Day 168	168	148 to 201

[#] Only in participants with abnormalities observed at EOT.

If more than one observation exists within the analysis window, the observation closest to the scheduled visit day will be selected for that visit. If there are two observations that have the same distance from the scheduled day, the value that is after the scheduled day will be selected in the analysis. If more than one observation are made on the same day, an average value if continuous or the worst value if categorical will be included in the analysis. The Follow Up visit will use the nominal follow-up visit with no windows defined.

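### The SAP tabulates a Day 7 ECG that the protocol does not schedule, and its other ECG windows lack a Day 1 time rule and an on-treatment condition

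*SAP*

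**What the plan says.** **Visits.** After Screening, SAP 3.5.4 has ECGs "performed on Day 1, Days 7, 14, 42, 84, every 42 days after Day 84, and EOT while the participant remains on study intervention". Protocol 8.3.3 says that they "will also be performed on Day 1, Days 14, 42, 84 and EOT, while the participant remains on study intervention". The ECG row of the Schedule of Activities (protocol 1.3) agrees with 8.3.3 on the absence of Day 7: the Day 2, 3, 7 and 28 cells are blank. SAP 2.1 records no modification of the protocol's analysis plan.

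**Windows.** In SAP Appendix 3, under "ECG for both IA and IM", the windows are Day 1 = 1, Day 7 = 2 to 9, Day 14 = 10 to 28, Day 42 = 29 to 63 and Day 84 = 64 to 105. Later windows apply to IM only. No window refers to treatment status. For several readings on one date the rule is: "If more than one observation are made on the same day, an average value if continuous or the worst value if categorical".

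**Baseline and Day 1.** SAP 3.5.4 takes the last pre-dose Screening ECG as baseline. During treatment, footnote n of the Schedule says that the "12-lead ECG is performed 15 minutes prior to the end of the first daily infusion or approximately 3 hours post oral dose", so the Day 1 ECG is an on-drug reading. Footnote a allows the two to share a date: "Day -1 can be the same calendar day as Day 1".

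**Follow-up.** Appendix 3 says: "The Follow Up visit will use the nominal follow-up visit with no windows defined".

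**The concern.** The 12-lead ECG is a named secondary safety variable, and the protocol synopsis lists arrhythmia due to QT shortening as a potential risk. SAP 6.6.4 plans summaries of ECG values and of change from baseline by time point. With one arm, change from baseline is the only internal contrast, so no control group would expose an artefact of visit assignment. The interim analysis, on about 28 participants, uses the same methods, so a few misassigned readings could move a row.

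Three things could mislead. A Day 7 row would look like a scheduled visit but would describe whoever happened to have an ECG on Days 2 to 9. The first-dose change could be attenuated if the baseline reading is averaged into Day 1. The Day 42 and Day 84 rows could mix on-drug and off-drug readings.

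**Working it through.** The plan states no figure on this point, so there is none to reproduce. The check maps the protocol's ECG days onto the SAP windows.

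**1. Day 7 window (Days 2 to 9).**
- ECG days within the protocol's visit windows: Day 1; Day 14 ± 3 = 11 to 17; Day 42 ± 7 = 35 to 49; Day 84 ± 7 = 77 to 91. None lies in 2 to 9.
- EOT ECG, last dose on day L: if taken on day L, it falls in 2 to 9 for L = 2 to 9. With the ± 3 day EOT window, it can do so for L = 1 to 12.
- Follow-up ECG: the earliest is L + 21, which is at least Day 22, so never.
- What remains is unscheduled ECGs. Protocol 8.3 allows these for perceived safety issues. Protocol 8.3.3 has abnormal tracings repeated unless they are related to the underlying disease or confirmed as not clinically significant. Repeats of an abnormal Day 1 ECG are therefore one evident source, though the documents do not say how many to expect.

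**2. Day 1 averaging.** Let B be the pre-dose screening ECG and P the on-drug Day 1 ECG, both dated Day 1.
- Intended change: P - B.
- Tabulated change if the two are averaged: (B + P)/2 - B = (P - B)/2, exactly half.
- Example: B = 400 and P = 370 msec. The average is 385, so the change is -15 instead of -30 msec.
- The share s of participants affected is not given. If all had the same change d, the row mean would be d × (1 - s/2). With d = -30 msec:

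| s | tabulated mean change (msec) |
|---|---|
| 10% | -28.5 |
| 25% | -26.25 |
| 50% | -22.5 |
| 100% | -15 |

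**3. On-treatment condition.**
- Protocol 8.3.3 and SAP 3.5.4 limit the post-screening ECGs to participants on study intervention, apart from EOT (required for all) and Follow-up.
- In the Schedule, the Day 2 to Day 28 column headings carry footnote p (participants continuing on drug). The Day 42 and Day 84 headings do not, and neither do their ECG cells. The Day 42 eye-examination cell does.
- Protocol 6.1.1 requires responders who finish before Day 42 to return on Days 42 and 84. Read from the Schedule, they have an ECG; read from 8.3.3, they do not.
- If taken, such a reading falls in the Day 42 or Day 84 window. With the half-life of about 130 hours in protocol 2.2.4, a last dose on Day 42 leaves 2^(-1008/130) = 0.005, or 0.5%, by Day 84.
- Protocol 2.1 reports 40% lower clearance in Chinese participants. Assuming that 130 hours belongs to the higher clearance and that volume is unchanged, half-life is 130/0.6 = 217 hours and 2^(-1008/217) = 0.040 remains. The range is 0.5% to 4%.
- An EOT ECG 3 days after last dose differs: 2^(-72/130) = 68%, or 79% at 217 hours. It is not an off-drug reading.
- For non-IM participants, treatment ends by Day 84, so Days 85 to 105 (21 of the 42 days in the Day 84 window) are after the last permitted dose.

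**The case against.** The best defence is that only the Day 7 mismatch is a plain contradiction. Its likely result is a sparse row with its number of participants shown. That is fair as to size, but a sparse row labelled as a scheduled visit still misdescribes its source.

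On Day 1, the SAP assigns the Screening ECG to baseline and summarises change at post-baseline time points, and a pre-dose reading is not post-baseline. The comparison with vital signs, where Appendix 3 separates Day 1 by CRF date and time, is also imperfect: vital signs are taken before and after each Day 1 dose, and their baseline is itself a Day 1 reading. Both points stand. The SAP does not say that a baseline record may enter the Day 1 window, but it does not bar it either. The window and averaging rules applied as written would admit it.

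A reader might infer that Follow-up ECGs, taken only after an abnormal EOT ECG, spill into the Day 42 and Day 84 rows. By study day alone, a Follow-up 28 days after last dose would fall in the Day 42 window for last doses on Days 1 to 35 and in the Day 84 window for Days 36 to 77. The documents do not support this: Appendix 3 gives ECG Follow-up its own row with no window and says "The Follow Up visit will use the nominal follow-up visit with no windows defined". A reader might also conclude that the by-visit QTc changes are wrong in general. That too goes beyond the text, since each effect depends on which readings occur.

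**Conclusion.** The point holds as a consistency and specification problem that should be fixed before the tables are programmed.

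- **Day 7:** certain. The SAP defines a visit that the protocol does not schedule, and no ECG done within its protocol visit window other than an early EOT can fill it.
- **Day 1:** conditional. The tabulated change is halved in any participant whose screening ECG and first dose share a date, if the baseline record is also windowed to Day 1. The frequency is unknown.
- **Days 42 and 84:** the protocol's text and Schedule disagree on off-drug ECGs, and the windows would accept such readings. The number is unknown.

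The effect stops at descriptive by-visit ECG rows. The QTcF threshold counts in SAP 6.6.4, including decreases above 30 and 60 msec, use all post-baseline values and EOT, so they do not depend on these windows. The primary endpoint, TEAE incidence, is untouched, and no hypothesis is tested for efficacy.

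**What to change.** 1. Delete Day 7 from SAP 3.5.4 and from the ECG rows of Appendix 3. Keep early stoppers' EOT ECGs under EOT and list other Day 2 to 9 ECGs as unscheduled. If a Day 7 ECG was intended, the protocol schedule is the place to add it.
2. For ECG Day 1, use CRF date and time, as Appendix 3 does for vital signs. The pre-dose reading is baseline only, the on-dose reading is Day 1, and the two are never averaged.
3. Reconcile protocol 8.3.3 and SAP 3.5.4 with the Schedule on whether Day 42 and Day 84 ECGs are taken in participants who have stopped drug. Apply the on-treatment condition in the by-visit windows, define it by reference to the last dose date, and list any off-drug readings separately.
4. For clarity, add that Follow-up records do not enter the day windows. This only makes the present rule explicit.

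The cost is SAP wording and programming, plus a protocol clarification for item 3. Some by-visit rows will hold somewhat fewer readings. No protocol-scheduled on-treatment ECG is lost.

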3.5.5. Eye Examination

The examination will consist of visual acuity, confrontational visual field testing, and color perception testing. An eye examination will be conducted at Screening and EOT. If the participant is continuing on study intervention, an eye examination will also be performed on Days 14, 28 and 42. An eye examination will be performed at the Follow-up visit only if abnormal at EOT.

4. ANALYSIS SETS (POPULATIONS FOR ANALYSIS)

Data for all participants will be assessed to determine if participants meet the criteria for inclusion in each analysis population prior to unblinding and releasing the database and classifications will be documented per standard operating procedures (SOP).

Population	Description	Applicable Analysis (for additional information refer to section 6)
Enrolled	"Enrolled" means a participant's, or their legally authorized representative's, agreement to participate in a clinical study following completion of the informed consent process and assignment to study intervention. A participant will be considered enrolled if the informed consent is not withdrawn prior to participating in any study activity after screening. Potential participants who are screened for the purpose of determining eligibility for the study, but do not	

Population	Description	Applicable Analysis (for additional information refer to section 6)
	participate in the study, are not considered enrolled, unless otherwise specified by the protocol.	
Intent-to-Treat (ITT)	The ITT population consists of all enrolled participants who receive at least 1 dose of study intervention. The ITT is the primary efficacy population.	Key secondary endpoint, main analysis (Section 6.2.1.1) Secondary analyses and sensitivity/supplementary/subgroup analyses (Sections 6.2.1.2 - 6.2.2) Baseline and other summaries and analyses (Section 6.5)
Modified Intent-to-Treat (mITT)	The mITT population consists of ITT participants who had proven or probable IFD as determined by the investigators based on the definition specified in protocol Appendix 9, Section 10.9.	Key secondary endpoint, supplementary analysis (Section 6.2.1.2) Secondary analyses (Sections 6.2.2-6.2.4) Baseline and other summaries and analyses (Section 6.5)
Mycological Intent-to-Treat IA (myITT-IA)	The myITT-IA population consists of mITT participants with proven or probable IA based on cytology, histology, culture, or GM and assessed by the investigators.	Key secondary endpoint, supplementary analysis (Section 6.2.1.2) Secondary analyses (Sections 6.2.2-6.2.4) Baseline and other summaries and analyses (Section 6.5)
Mycological Intent-to-Treat IM (myITT-IM)	The myITT-IM population consists of mITT participants with proven or probable IM based on cytology, histology, culture, or GM and assessed by the investigators.	Exploratory analysis (Sections 6.3.1-6.3.3) Baseline and other summaries and analyses (Section 6.5)
Safety Population	The safety population consists of all enrolled participants who receive at least 1 dose of study intervention.	Primary and Secondary safety endpoints analyses (Section 6.1, 6.6)

Population	Description	Applicable Analysis (for additional information refer to section 6)
Pharmacokinetic (PK) Concentration Analysis Set	All participants who are treated and have at least 1 measurable PK concentration data, and who have no major protocol violations that can have an effect on their PK data.	Secondary analysis (Section 6.2.5) Exploratory analysis (Section 6.3.4)

